# 10.6 Secondary Malignancy

A secondary malignancy is a cancer caused by treatment for a previous malignancy (e.g., treatment with investigational agent/intervention, radiation or chemotherapy). A secondary malignancy is not considered a metastasis of the initial neoplasm.

CTEP requires all secondary malignancies that occur following treatment with an agent under an NCI IND/IDE be reported expeditiously via CTEP-AERS. Three options are available to describe the event:

- Leukemia secondary to oncology chemotherapy (e.g., acute myelocytic leukemia [AML])
- Myelodysplastic syndrome (MDS)
- Treatment-related secondary malignancy

Any malignancy possibly related to cancer treatment (including AML/MDS) should also be reported via the routine reporting mechanisms outlined in each protocol.

# 10.7 Second Malignancy

A second malignancy is one unrelated to the treatment of a prior malignancy (and is **NOT** a metastasis from the initial malignancy). Second malignancies require **ONLY** routine AE reporting unless otherwise specified.

# 11 STUDY CALENDAR

Baseline/screening evaluations are to be conducted within 4 weeks (28 days) prior to start of protocol therapy. Scans must be done <4 weeks (28 days) prior to the start of protocol therapy. In the event that the patient's condition is deteriorating, laboratory evaluations should be repeated within 48 hours prior to initiation of the next cycle of therapy.

DOSE FINDING (ARM A): Priming, Safety Lead-In and Treatment Cycles 												
			Treatment					Follow Up				
Treatment Cycles/Visits	Screening	Week 1	Safety Lead-In		Cycle 1		Cycle 2	and subsec	quent cycles	End of	~ . .	Follow Up 
	~ · · · · · · · · · · · · · · · · · · ·	Priming	Week 2-3	We	ek 1	Weeks 2-3	We	ek 1	Weeks 2-3 	Therapy	Safety	
Scheduling Window	Within 28 days	Day 1	Day 1 ±1 day	Day 1 ±2 days	Day 2-5 ±2 days	Day 1 ±2 days	Day 1 ±2 days	Day 2-5 ±2 days	Day 1 ±2 days	Within 10 days after last IP dose	30 days after last IP dose ±7 days	Month 2, 4, 6, 9, 12 and annually (Year 2-5)
Administrative Procedures												
Informed consent/assent	X											
Eligibility evaluation	X											
Medical history 	X	X	X	X	X	X	X	X	X	X	X	X
Concomitant medications 	X	X	X	X	X	X	X	X	X	X	X	
Treatment												
Hu5F9-G4 (magrolimab) administration 		X	X	X		X	X		$X^4$			
Dinutuximab administration 					X			X				
Clinical Assessments												
Height, weight 	X	X		X			X			X	X	
Physical exam 	X	X	X	X			X			X	X	X
Vital signs 	X	X	X	X	X	X	X	X	X	X	X	
ECG	X											
ECHO, MUGA or Cardiac MRI	X											
Performance status 	X	X		X			X				X	
Disease evaluation 	X	End of Cycle 2 and 4, and then after every 4 cycles								X		
Confirmatory imaging 					As	per Section Er	ror! Referen	nce source 1	not found.			

End of Cycle 2, 4, 8 and 12

Χ

THIS PROTOCOL IS FOR RESEARCH PURPOSES ONLY, SEE PAGE 1 FOR USAGE POLICY

#### DOSE FINDING (ARM A): Priming, Safety Lead-In and Treatment Cycles **Treatment** Follow Up **Treatment Cycles/Visits** Week 1 Safety Lead-In Cycle 1 Cycle 2 and subsequent cycles End of Screening Follow Up Safety Therapy **Priming** Week 2-3 Week 1 Weeks 2-3 Week 1 Weeks 2-320 Month 2, 4, 6, Within 10 30 days after Within 28 Day 1 Day 1 Day 2-5 Day 1 Day 1 Day 2-5 Day 1 9, 12 and **Scheduling Window** Day 1 days after last IP dose ±1 day ±2 days ±2 days ±2 days ±2 days ±2 days ±2 days annually days last IP dose ±7 days (Year 2-5) Bone marrow aspiration and biopsy if NBL/ X -----→ End of Cycle 2 and 4, and then after every 4 cycles X ganglioneuroblastoma AE and SAE evaluation Continuously Clinical Laboratory Tests Pregnancy test X As required locally CBC with differential and Χ $X^{22}$ $X^{22}$ Χ X X platelets Electrolytes, creatinine, urea (BUN), Ca2+, PO4, X X X X X X $Mg^{2+}$ ALT, AST, bilirubin Χ X X X X Amylase, lipase, CRP Χ Χ Blood cell ABO phenotyping (minor X -----→ antigens) Type and screen x -----→ (ABO/rhesus) 15 Direct Antiglobulin Test X -----→ (DAT) [direct Coombs test]15 Urinalysis Correlative Exploratory Biology Studies Tumor tissue specimen X - As available X Blood samples X X Χ X Χ Χ Χ

Version Date: 02/02/2024 Page 96

X -----→

Bone marrow aspirate

# CHILDREN'S ONCOLOGY GROUP

#### PED-CITN-03

THIS PROTOCOL IS FOR RESEARCH PURPOSES ONLY, SEE PAGE 1 FOR USAGE POLICY

- Arm A included the priming dose plus single agent Safety Lead-In conducted over 21 days, then treatment cycles (21-day cycle) begin. Cycles may be repeated as long as the patient does not have unacceptable toxicity (see Section 6.3 or Section Error! Reference source not found.) or disease progression to a maximum of 12 cycles.
-  Standard medical history is acceptable. Following screening, updates to medical history should be recorded.
- Prior and concomitant medications All medications taken within 21 days prior to treatment initiation and all new medications, including all medications for AEs, taken up to 30 days after treatment discontinuation should be recorded.
- Hu5F9-G4 (magrolimab) will be administered as a priming dose, single agent Safety Lead-In and Day 1 of every week of every 3 week Cycles as outlined in Section 6.2. A premedication regimen (oral acetaminophen and diphenhydramine, or comparable regimen) is required before the initial doses of Hu5F9-G4 (magrolimab) and in case of re-priming of the patient after > 4 weeks interruption in treatment.
- Dinutuximab will be administered on Days 2-5 during the first week of every cycle as specified in Section 6.2. Administer antihistamines, antipyretics (i.e., acetaminophen and ibuprofen) and analgesia prior to each dinutuximab infusion as per Section 6.2.
-  Both height and weight will be recorded at screening. Only weight will be recorded at subsequent applicable visits.
- A complete physical examination as well as a cancer-specific physical exam will be performed at screening. Physical exams at subsequent applicable visits will be targeted based on the investigator's clinical observations and symptomatology. If a physical exam is performed within 3 days prior to a subsequent dosing day it does not need to be repeated on the dosing day provided there is no new status change.
- Vital signs = heart rate, respiratory rate, blood pressure, temperature, pulse oximetry. See Section 6.2.1.3 and 6.2.1.4 for collection timepoints during and after infusion. Vital signs must also be collected at each non-dosing visit.
-  Karnofsky score of ≥50% is required for patients >16 years, and Lansky score of ≥50% is required for patients ≤16 years. Patients unable to walk due to paralysis, but who are using a wheelchair, will be considered ambulatory for the purpose of assessing the performance score. See APPENDIX A.
- Baseline disease evaluation will occur within 28 days of treatment initiation. During the treatment period Cycles 1 through 4, patients should be re-evaluated for response at the end of Cycles 2 and 4. After Cycle 4, disease evaluation will occur every 12 weeks (after every 4 cycles). Disease evaluations should occur within 7 days prior to dosing of the subsequent cycle. If treatment is delayed, disease evaluations will follow the originally scheduled calendar dates and should not be adjusted for the dose delay. The same method of assessment and technique should be used throughout the study. See Section 12 for disease parameters, methods of assessment, and response criteria. For patients with neuroblastoma/ganglioneuroblastoma, bilateral bone marrow aspirates and trephine biopsies are required at all disease assessment time points (see Section 12.2) and Follow-up Visits for disease evaluation.
- Confirmatory scans should also be performed according to Section 12 in patients with measurable disease. The same method of assessment and technique should be used throughout the study.
- All AEs occurring within 30 days after the last dose of the study drug must be reported in a routine manner using Rave. Additionally, all AEs that occur within 30 days after the last dose of the study drug, regardless of causality, meeting the expedited reporting criteria outlined in Section 10.3 must also be reported expeditiously via CTEP-AERS.
- All clinical laboratory tests must be performed in a licensed laboratory according to local policy. Pregnancy tests may be performed at the site using a licensed test. Laboratory results outside the limits of eligibility may be repeated to confirm eligibility and must be within the limits of eligibility before treatment initiation. Clinical laboratory tests conducted during screening do not need to be repeated on C1D1 if completed within 7 days prior to treatment initiation. All clinical laboratory tests during the treatment period must be performed within 72 hours prior to dosing. If treatment is delayed all clinical laboratory tests (and their respective windows) will adjust with the dose delay to reflect the patient's clinical status at the time of dosing.
- Females of childbearing potential must have a negative urine or serum pregnancy test within 30 days of enrollment and within 72 hours prior to treatment initiation. Additional pregnancy tests (serum or urine) should be obtained throughout the study in accordance with local policy.
- Specimen **must** be drawn, completed, resulted and active per institutional guidelines prior to the Priming dose of Hu5F9-G4 (magrolimab). ABO, Rh, and DAT may be pan-reactive due to Hu5F9-G4 (magrolimab) binding to red cells (see Section 7.2.4).

THIS PROTOCOL IS FOR RESEARCH PURPOSES ONLY, SEE PAGE 1 FOR USAGE POLICY

- Upon treatment discontinuation, patients will complete the Safety Visit within 30 (±7) days, and Follow-up Visits at month 2 (± 1 week), month 4 (± 2 weeks), month 6 (± 4 weeks), month 9 (± 4 weeks), and month 12 (± 2 months) and then yearly (± 2 months) until year 5, or until disease progression or until death, lost to follow-up, withdrawal of consent, or the end of the study, whichever occurs first. If a subsequent anti-cancer therapy is to be administered after treatment discontinuation but before the scheduled Safety Visit, the Safety Visit assessments should be conducted prior to the start of the new therapy if possible.
  - Follow-up Visits will be completed in-person unless the patient does not agree to continue in-person visits. In this case telephone contact may be arranged to ensure the collection of as many safety and efficacy parameters as possible. A patient that agrees to modified follow-up is not considered to have withdrawn consent or to have withdrawn from the study.
  - Patients removed from protocol therapy for unacceptable AE(s) will be followed until resolution or stabilization of the AE. In addition, these patients will complete the EOT, Safety, and Follow-up Visits according to protocol.
- All blood draws for correlative exploratory biology studies will be performed according to the schedule outlined in Table 3, Specimen Collection Schedule; and Section 5. All blood draws for correlative exploratory biology studies must be performed prior to dosing. If treatment is delayed, blood draws for correlative exploratory biology studies will follow the originally scheduled calendar dates and should not be adjusted for the dose delay.
- Archival slides will be requested from all patients. If available, clinical biopsies or surgical samples obtained during treatment or at disease progression will be requested.
-  After Cycle 2, Hu5F9-G4 (magrolimab) will be administered ONLY on Day 1 of week 1 and 3 only (week 2 will be a week of rest).
- Bone marrow aspirations will be conducted in all patients with neuroblastoma/ganglioneuroblastoma (as per INRC). Week 1, Day 1 collection is mandatory, *except* if viably frozen bone marrow aspirate collected within 4 weeks (28 days) of the Priming dose (Week 1, Day 1) is available and can be provided to the EET Biobank. Bone marrow aspirates are required at all disease assessment timepoints (end of Cycle 2, 4, 8 and 12). Bone marrow aspirate at End of Therapy is optional.
- Within 24 hours prior to the Priming dose (Week 1) of Hu5F9-G4, hemoglobin must be ≥ 9.5 g/dL. Within 24 hours prior to the first full dose (Week 2) of Hu5F9-G4, hemoglobin must be ≥ 9.0 g/dL (see Section 6.2.1.3). Hemoglobin must be checked 3 to 6 hours after the initiation of the first and second doses of Hu5F9-G4 (magrolimab).

THIS PROTOCOL IS FOR RESEARCH PURPOSES ONLY, SEE PAGE 1 FOR USAGE POLICY

Baseline/screening evaluations are to be conducted within 4 weeks (28 days) prior to start of protocol therapy. Scans must be done < 4 weeks (28 days) prior to the start of protocol therapy. In the event that the patient's condition is deteriorating, laboratory evaluations should be repeated within 48 hours prior to initiation of the next cycle of therapy.

Treatment Cycles/Visits	Screening	Treatment								Follow Up		
		Priming Cycle 1				Cycle 2 and subsequent cycles			End of	G 6 /	E II II 17	
		Week 1	Week 2		Weeks 3-4	Week 1		Weeks 2-3 	Therapy	Safety	Follow Up 	
Scheduling Window	Within 28 days	Day 1	Day 1 ±2 days	Day 2-5 ±2 days	Day 1 ±2 days	Day 1 ±2 days	Day 2-5 ±2 days	Day 1 ±2 days	Within 10 days after last IP dose	30 days after last IP dose ±7 days	Month 2, 4, 6, 9, 12 and annually (Year 2-5)	
Administrative Procedures												
Informed consent/assent	X											
Eligibility evaluation	X											
Medical history 	X	X	X	X	X	X	X	X	X	X	X	
Concomitant medications 	X	X	X	X	X	X	X	X	X	X	X	
Treatment												
Hu5F9-G4 (magrolimab) administration 		X	X		X	X		$X^{20}$				
Dinutuximab administration 				X			X					
Clinical Assessments												
Height, weight 	X	X	X			X			X	X	X	
Physical exam 	X	X	X			X			X	X	X	
Vital signs 	X	X	X	X	X	X	X	X	X	X	X	
ECG	X											
ECHO, MUGA or Cardiac MRI	X											
Performance status 	X	X	X			X				X	X	
Disease evaluation 	X	_	End of Cycle 2 and 4, and then after every 4 cycles								X	
Confirmatory imaging 				-	As į	per Section I	Error! Refere	ence source not	found.			
Bone marrow aspiration and biopsy if NBL/ganglioneuroblastoma 10, 21	X									X		
AE and SAE evaluation 							Continuo	ısly			1	
Clinical Laboratory Tests 												

Version Date: 02/02/2024

THIS PROTOCOL IS FOR RESEARCH PURPOSES ONLY, SEE PAGE 1 FOR USAGE POLICY

Treatment Cycles/Visits	Screening				Follow Up						
		Priming	Cycle 1			Cycle 2 and subsequent cycles			End of	G C .	E II II 17
		Week 1	Week 2		Weeks 3-4	Week 1		Weeks 2-3 	Therapy	Safety	Follow Up 
Scheduling Window	Within 28 days	Day 1	Day 1 ±2 days	Day 2-5 ±2 days	Day 1 ±2 days	Day 1 ±2 days	Day 2-5 ±2 days	Day 1 ±2 days	Within 10 days after last IP dose	30 days after last IP dose ±7 days	Month 2, 4, 6, 9 12 and annually (Year 2-5)
Pregnancy test 	X	As required locally									
CBC with differential and platelets	X	$X^{22}$	X 			X				X	
Electrolytes, creatinine, urea (BUN), Ca 2+ , PO 4  , Mg 2+	X	X	X			X				X	
ALT, AST, bilirubin	X	X	X			X				X	
Amylase, lipase, CRP	X	X	X			X					
Blood cell ABO phenotyping (minor antigens) 	X→										
Type and screen (ABO/rhesus) 	X	X→									
Direct Antiglobulin Test (DAT) [direct Coombs test]	X	>									
Urinalysis	X										
Correlative Exploratory Biol	logy Studies										
Tumor tissue specimen 	X	X - As available									
Blood samples 		X	X	X	X	X	X	X	X		
Bone marrow aspirate 	X	→	→ End of Cycle 2, 4, 8 and 12					8 and 12	X		

Arm B patients will receive the priming dose followed by Cycle 1 and 2 (each 21 days). Cycles may be repeated as long as the patient does not have unacceptable toxicity (see Section 6.3 or Section Error! Reference source not found.) or disease progression to a maximum of 12 cycles for patients in cohorts B1, B2 and B3 and to a maximum of 5 cycles post resection for patients in cohort B4.

Standard medical history is acceptable. Following screening, updates to medical history should be recorded.

Prior and concomitant medications – All medications taken within 21 days prior to treatment initiation and all new medications, including all medications for AEs, taken up to 30 days after treatment discontinuation should be recorded.

Hu5F9-G4 (magrolimab) will be administered as a priming dose, single agent Safety Lead-In and Day 1 of every week of every 3 week Cycles as outlined in Section 6.2. A premedication regimen (oral acetaminophen and diphenhydramine, or comparable regimen) is required before the initial doses of Hu5F9-G4 (magrolimab) and in case of re-priming of the patient after > 4 weeks interruption in treatment.

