for archived tissue for analysis. Within 4 weeks after the initial resection, patients will receive the priming dose of Hu5F9-G4 (magrolimab) on Day 1, followed by Cycle 1 in week 2 with Hu5F9-G4 (magrolimab) administered at RP2D on Day 1 and dinutuximab 17.5 mg/m² on Days 2-5, followed by Hu5F9-G4 (magrolimab) at RP2D on Day 1 of weeks 3 and 4 until the second resection (see Table 6 below). Upon recovery from the second resection, the cycles may be repeated to a maximum of 5 cycles (adjuvant therapy). If the cycles are restarted within 4 weeks of the last dose of Hu5F9-G4 (magrolimab), the patient will pick up the regimen as per the next scheduled regimen cycle as per Table 6. If restarting the regimen is delayed beyond 4 weeks of the last dose of Hu5F9-G4 (magrolimab), the patient will restart as per Table 7 and will require a re-priming dose of Hu59-G4 (magrolimab) with repeat of cycle 1 and 2 with weekly dosing of Hu5F9-G4 (magrolimab).

Table 6: Regimen Description for Arm B - Expansion Cohorts B1 - B3 (Confirmed Neuroblastoma, Evaluable Neuroblastoma, Measurable Osteosarcoma), Cohort B4 (Resectable, pulmonary only relapsed osteosarcoma\*\*) - Non-staged resections and Cohort B4 - Staged resections prior to surgery and post resection with restart within 4 weeks of last dose

Agent	Premedications; Precautions	Dose	Route	Schedule	Cycle Length
Hu5F9-G4 (magrolima b)	Administer according to guidelines in Section 6.2.1.3. Acetaminophen oral (PO) and diphenhydramine (IV) or a comparable regimen up to 15 minutes before the first two doses of Hu5F9-G4 (magrolimab), and in case	650 mg) of acetaminophen; 0.5 - 1 mg/kg (max 50 mg) of diphenhydrami	PO; Diphenhydramin	Priming: Day 1 Week 1	
	of re-priming of the patient after > 4 weeks interruption in treatment.	Hu5F9-G4 (magrolimab) 1 mg/kg	IV (peripheral or central line) over 3 hours (± 30 min)		
	Monitor for infusion reactions during and for 1-hour post infusion during the priming dose. Any patients experience AEs during this period should be monitored as clinically indicates for up to 24 hours post infusion. Treatment of infusion reactions will be according to standard operating procedures.	Hu5F9-G4 (magrolimab) RP2D mg/kg*	infusions: Infuse IV over 2 hours (± 10 min)	Cycle 1: Day 1, Weeks 2, 3 and 4 Cycle 2: Day 1, Weeks 1, 2 and 3 Cycle 3 and subsequent cycles: Day 1 of Weeks 1 and 3 of each cycle (Week 2 is skipped)**	21 days (3 weeks)

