- Gabapentin doses can be increased further if necessary; institutional guidelines should be followed.

Lidocaine dosing should follow institutional standards; however, the following dosing may be considered:

- Initiate continuous infusion at 1 mg/kg/hour (bolus) with the continuous infusion rate of is 0.5 -2 mg/kg/hour.
- Lidocaine levels should initially be checked every 8 hours (Q8h) but may be spaced out once therapeutic concentrations have been achieved. Dose should be titrated in 25% increments to achieve therapeutic serum concentrations (goal 2-4 mcg/mL).
- Consider dose reduction in patients with hepatic disease.
- Premedications for infusion reactions
  - Antihistamines and Antipyretics

Administer an antihistamine such as diphenhydramine (0.5 to 1 mg/kg; maximum dose 50 mg) intravenously over 10 to 15 minutes starting 20 minutes prior to initiation of dinutuximab and as tolerated every 4 to 6 hours during the dinutuximab infusion, as per institutional guidelines.

Acetaminophen

Administer acetaminophen (10 to 15 mg/kg/dose; maximum dose 650 mg) PO approximately 20 minutes prior to each dinutuximab infusion and every 4 to 6 hours as needed for fever or pain, or as per institutional guidelines.

Ibuprofen

Administer ibuprofen (5 to 10 mg/kg/dose) every 6 hours as needed for control of persistent fever or pain, as per institutional guidelines.

• Monitoring Procedures

Vital signs (heart rate, respiratory rate, blood pressure, temperature, pulse oximetry) will be collected prior to the beginning of dinutuximab infusion (within 30 minutes) and every 30 (±10) minutes for the first hour of infusion, and then hourly during infusion, or as clinically indicated. Post-infusion, vital signs and AEs will be collected every 30 (±10) minutes twice, then hourly (±20) minutes for a total of 4 hours. For patients who previously tolerated the study agent without infusion-related reactions, the post-infusion monitoring period may be reduced at the discretion of and documented by the treating physician.

Document intake and output on the day of dinutuximab administration.

Standard imaging will be performed for disease assessment where indicated and according to the protocol schedule (screening, disease assessment at the conclusion of Cycle 2 and 4 and then every 4 cycles) (see Section 11).

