#### 6.7 General Concomitant Medication

Medications, including reason for use, date(s) of administration, and dosage information, taken within 28 days prior to the start of treatment will be recorded. Concomitant medications, including medications for AEs, will continue to be recorded up to 30 days after treatment discontinuation. This includes any medication or vaccine, including over-the-counter or prescription medicines, vitamins, and/or herbal supplements. The investigator should be alerted if the patient is taking any agent known to affect the study agent(s) or with the potential for drug interactions. Following treatment discontinuation, information on subsequent anti-cancer therapies will be recorded.

Because there is a potential for interaction of Hu5F9-G4 (magrolimab) and Dinutuximab with other concomitantly administered drugs, the case report form must capture the concurrent use of all other drugs, over-the-counter medications, or alternative therapies. The Principal Investigator should be alerted if the patient is taking any agent known to affect or with the potential for drug interactions. The study team should check a frequently updated medical reference for a list of drugs to avoid or minimize use of.

For all prohibited and/or restricted concomitant medications, treatment and supportive care while receiving protocol therapy, please refer to inclusion/exclusion criteria (section 3.0).

Pharmacologic doses of systemic corticosteroids should be used ONLY for life-threatening conditions (i.e. life-threatening allergic reactions and anaphylaxis such as bronchospasm, stridor) unresponsive to other measures. The use of dexamethasone as an anti-emetic is not permitted. Corticosteroid therapy can be used as a premedication for transfusion in patients known to have a history of transfusion reactions or for treatment of an unexpected transfusion reaction (hydrocortisone 2 mg/kg or less or an equivalent dose of an alternative corticosteroid). The use of steroids during protocol therapy requires clear justification and documentation.

Patients who use oral contraceptives should continue their use. Males and females of reproductive potential should use highly effective means of contraception (refer to section 6.8).

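### Footnotes 3, 4 and 5 of both study calendars conflict with other current text on magrolimab frequency, ibuprofen timing and the prior-medication look-back

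*Combined protocol and SAP*

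**What the plan says.** Section 11 has one calendar for Arm A and one for Arm B, and footnotes 3, 4 and 5 are essentially the same in both.

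- **Magrolimab.** Footnote 4 reads "Hu5F9-G4 (magrolimab) will be administered as a priming dose, single agent Safety Lead-In and Day 1 of every week of every 3 week Cycles" and refers the reader to Section 6.2. Footnote 20 of the Arm A calendar reads "After Cycle 2, Hu5F9-G4 (magrolimab) will be administered ONLY on Day 1 of week 1 and 3 only", and the Arm B footnote 20 says the same. Table 6 in Section 6.2.1.2 has "Cycle 3 and subsequent cycles: Day 1 of Weeks 1 and 3 of each cycle (Week 2 is skipped". Section 6.1.1.2 (Arm A), Section 6.4 (expansion cohorts) and the notes to the schema agree with footnote 20.
- **Ibuprofen.** Footnote 5 reads "Administer antihistamines, antipyretics (i.e., acetaminophen and ibuprofen) and analgesia prior to each dinutuximab infusion as per Section 6.2". Section 6.2.1.4 reads "Administer ibuprofen (5 to 10 mg/kg/dose) every 6 hours as needed for control of persistent fever or pain". The dinutuximab premedication entry in Table 6 names acetaminophen, diphenhydramine and analgesia, but not ibuprofen.
- **Prior medications.** Footnote 3 asks for medications from the 21 days before treatment starts. Section 6.7 asks for those "taken within 28 days prior to the start of treatment will be recorded".

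**The concern.** Each footnote states a rule of its own and does not merely point to the body text, so the protocol carries two current instructions on each item. For magrolimab they give different exposure from Cycle 3 onward. For ibuprofen they differ on whether the drug is scheduled or given only when needed. For prior medications they differ on how far back the site must record.

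If sites resolved these conflicts differently, patients in one cohort could have different late-cycle magrolimab exposure, different background use of an anti-inflammatory drug and records of different completeness. Adverse events and responses arising after Cycle 2 would then be summarised across that variation with nothing in the plan to flag it.

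**Working it through.** The plan states no total number of magrolimab doses, so there is no figure to reproduce. The check is a count at the maximum duration, followed by side-by-side comparison.

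**Magrolimab doses, excluding priming and lead-in doses**

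Inputs:
- Maximum cycles: 12 for Arm A (footnote 1: "disease progression to a maximum of 12 cycles") and for B1-B3; 5 after resection for B4.
- Footnote 4: 3 doses in every 3-week cycle.
- Table 6, Section 6.1.1.2 and footnote 20: 3 doses in each of Cycles 1 and 2, then 2 per cycle.

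The count does not use Table 5, because its magrolimab schedule entry cannot be read in the available text.

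For C cycles (C of 2 or more), footnote 4 gives 3C and the other text gives 2 x 3 + 2(C - 2).
- C = 12: 3 x 12 = 36 against 6 + 20 = 26. The difference is 10 doses, and 10/26 = 38%.
- C = 5: 3 x 5 = 15 against 6 + 6 = 12. The difference is 3 doses, and 3/12 = 25%.
- Cycles 1 and 2 alone: 6 against 6, no difference.

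Priming and lead-in doses add equally to both sides. Arm A becomes 39 against 29 (3 added) and B1-B3 become 37 against 27 (1 added). The five-cycle B4 count leaves out cycles that staged-resection patients receive before their second operation.

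Section 6.3 assesses dose-limiting toxicity in the lead-in and Cycle 1. Both fall before the two readings diverge.

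**How the calendars key the row**

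In both arms the Weeks 2-3 column header for Cycle 2 and later carries footnote 20. The magrolimab cell beneath it carries footnote 4 in Arm A and footnote 20 in Arm B. The Arm B copy of footnote 4 also lists a single-agent Safety Lead-In. Section 6.2.1.2 and the Arm B calendar columns show no such period: Arm B goes from priming straight to Cycle 1.

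**Ibuprofen**

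Dinutuximab is given on Days 2-5, which is 4 infusions per cycle. Footnote 5 therefore implies 4 pre-infusion ibuprofen administrations per cycle. Section 6.2.1.4 schedules none, and the Table 6 premedication list does not include the drug.

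**Prior medications**

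28 - 21 = 7 days. Section 6.7 includes vaccines among the medications to record, and exclusion 3.2.11 bars a live vaccine in the 28 days before treatment. A 21-day record leaves days 22-28 of that window undocumented on the medication form.

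**The case against.** The strongest reply concerns magrolimab. Footnote 4 defers to Section 6.2, footnote 20 sits on the column header in both arms and is emphatic, and every other statement of the schedule agrees with it. A site would have to overlook all of these to give 36 doses. Section 6 describes the calendars as outlining the timing of procedures and visits, while the regimen itself is in Section 6.2. The central monitoring plan (Appendix V) also checks total magrolimab dose against the administration record at Cycles 2 and 4, so extra doses in Cycles 3 and 4 could be noticed. All of this stands, and it makes widespread misdosing unlikely. It does not remove the conflict: two footnotes to one table disagree, neither is given precedence, and the frequency in footnote 4 is not the one in the section it cites.

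On ibuprofen, Section 6.2.1.4 places the drug under its heading on premedication for infusion reactions, which may be where footnote 5 came from. The instruction under that heading is still as needed.

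On the look-back, footnote 3 cites no other section, so it does not misquote a source. It simply disagrees with Section 6.7. No stated analysis uses the extra 7 days.

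A reader might infer more: that sites dose from the calendar and cohorts will therefore mix regimens, that Arm A readers see only the weekly rule, or that footnote 5 exposes patients to harm. The documents do not support the first, for the reasons above. The second fails because the Arm A column header carries footnote 20. The third is a clinical judgement between two texts, which this point does not make.

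**Conclusion.** The three footnotes are wrong as written in the sense that each contradicts other current text. The magrolimab conflict is worth 10 doses (36 against 26) for a patient in Arm A or B1-B3 who completes 12 cycles, and 3 doses (15 against 12) over five B4 cycles. It is smaller for anyone who stops sooner and nil through Cycle 2. These figures assume that footnote 4 is read literally and that no doses are missed. They bound the disagreement between the texts and do not predict what sites will do. The ibuprofen conflict is scheduled against as-needed use, and the look-back conflict is 7 days of recording. The dose-limiting toxicity assessment, sample sizes, response thresholds and error rates are unaffected. The case for correcting the footnotes is that conflicting dosing, premedication and recording instructions can be removed at almost no cost.

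**What to change.** In one amendment, covering both calendars:

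- Reconcile footnote 4 with footnote 20, Table 6 and Sections 6.1.1.2 and 6.4, so that magrolimab frequency after Cycle 2 is stated once. The clinical team decides which text stands.
- Use the same footnote key for the Weeks 2-3 magrolimab cell in both calendars.
- Delete the single-agent Safety Lead-In from the Arm B copy of footnote 4.
- Reconcile footnote 5 with Section 6.2.1.4 and the Table 6 premedication list on ibuprofen. Again the clinical team decides.
- Give one look-back period in footnote 3 and Section 6.7, long enough to cover the 28-day live-vaccine window of exclusion 3.2.11.

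The cost is footnote and cross-reference wording, plus any matching change to the medication form's instructions. The design and the analysis do not change.
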